To tailor EMPOWER to the veteran population, our research team worked with VHA patients, physicians, and administrators; we then worked with software developers to convert the intervention to a computer-delivered format we call EMPOWER for Veterans (Electronic Version). This protocol describes how EMPOWER for Veterans will be tested in a randomized clinical trial evaluating whether it is effective with a markedly different population and format than in the initial Canadian study. The primary hypotheses of the RCT are that long-term users of benzodiazepines who are assigned to receive EMPOWER for Veterans will be significantly more likely than controls to cease taking benzodiazepines or reduce their benzodiazepine dose by at least 25% at six-month follow-up. The secondary hypotheses are that relative to controls, participants receiving EMPOWER for Veterans will improve more on anxiety symptoms, sleep quality, and overall health/quality of life at six-month follow-up. As functional outcomes were not measured in the original EMPOWER study, this is a unique contribution of the present trial. In addition to being important in themselves, these three secondary outcomes may moderate or mediate participants' response to EMPOWER for Veterans. For example, if secondary outcomes improve upon benzodiazepine tapering, participants may be more likely to continue to full cessation. In contrast, if functional outcomes deteriorate, patients and their physicians may be inclined to abandon EMPOWER for Veterans; if this were a common result it would likely reduce the adoption of EMPOWER for Veterans within VHA. Also, part of our secondary analysis will be to explore whether any effects of EMPOWER for Veterans observed on our primary outcomes at six-month follow-up are maintained at 12-month follow-up.

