5.6 Data Analysis

The randomization scheme will be checked by comparing key baseline measures between the experimental and the control group. If significant differences between groups are identified, we will adjust for these variables in all the models. Baseline variables that are strongly associated with the outcomes will also be included in the corresponding outcome models. Linearity between continuous variables and outcomes will be checked. If the relationship is not linear, other appropriate functional forms (e.g., quadratic) will be used or the variable will be changed to categorical. Proportions of missing values will be assessed, and a multiple imputation method will be used to impute the missing values if necessary and if the missing at random assumption is deemed reasonable.

Descriptive statistics will be calculated to examine data distributions. Tests for distributional assumptions (e.g., normality) for continuous variables will also be performed. Bivariate analyses will be performed for categorical variables using a Chi-square test, for continuous normally

distributed variables using independent t-test and for non-normally distributed continuous variables using nonparametric Wilcoxon rank-sum test.

For multivariate analysis for the main outcomes of benzodiazepine discontinuation and 25% dose reduction at follow-ups, we will use generalized estimating equations (GEE) models or generalized linear mixed models to examine the effect of EMPOWER for Veterans on the proportions of participants with discontinuation and dose reduction with logit link and compound symmetry correlation structure (in GEE) due to repeated measures within each participant. All the models will include the indicator variable for the EMPOWER for Veterans versus control conditions, time representing six- and 12- month follow-ups and covariates identified in bivariate analysis. The baseline benzodiazepine use (i.e., average daily dose) variable will also be included. The interaction between the indicator variable and time will be checked and dropped if non-significant at the significance level of 0.05.

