The same method will be used to examine any impact of the intervention on the three secondary outcomes at baseline and six-month follow-up (anxiety, sleep quality, and quality of life) with identity link and the same correlation structure if the normality assumption is met. Should the normality assumption be violated, other distributions and link functions will be specified. The models will include the same indicator variable for EMPOWER for Veterans versus the control condition, time for baseline and 6-month follow-up and covariates identified in bivariate analysis. Same interaction term will be checked and dropped if non-significant. SAS 9.4 will be used in all the analyses.

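### For anxiety, sleep quality and quality of life, the plan drops the group-by-time term when it is non-significant, although that term is the secondary hypothesis and baseline is one of the two time points

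*Combined protocol and SAP*

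**What the plan says.** Section 2.0 states the secondary hypothesis: relative to controls, "participants receiving EMPOWER for Veterans will improve more on anxiety symptoms, sleep quality, and overall health/quality of life at six-month follow-up". Section 3.0 repeats it without the time point.

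For these three outcomes, section 5.6 carries over the method of the primary models, with an identity link and compound symmetry if normality holds. It specifies: "The models will include the same indicator variable for EMPOWER for Veterans versus the control condition, time for baseline and 6-month follow-up", plus covariates. It then adds: "Same interaction term will be checked and dropped if non-significant".

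The level comes from the description of the primary models: "The interaction between the indicator variable and time will be checked and dropped if non-significant at the significance level of 0.05". The time variable there is different: "time representing six- and 12- month follow-ups and covariates identified in bivariate analysis".

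The only other arm comparison in section 5.6 is the bivariate step, with chi-square tests for categorical variables and, for continuous ones, the t-test or its rank-based substitute ("distributed variables using independent t-test and for non-normally distributed continuous variables using nonparametric Wilcoxon rank-sum test").

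**The concern.** In a model with group, time (baseline, 6 months) and their interaction, the interaction coefficient is the between-group difference in change. That is what improving more than controls means. Removing it at p > 0.05 removes the hypothesis from the model, not a nuisance term.

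The rule appears to have been carried over from the primary models. There both time points follow randomisation, so a group term without the interaction is still a treatment effect. Here one time point precedes randomisation.

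Section 5.6 does not say what is read after the drop. There are two possibilities:

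- **Reading (a):** the remaining group term is taken as the effect. It averages a baseline difference expected to be zero with the 6-month difference, so it is diluted.
- **Reading (b):** the drop is taken to mean no effect. Nothing is diluted, but no estimate or interval is part of the planned result.

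What is reported for each outcome then depends on a p-value and on an unstated choice. Section 2.0 says that deterioration in these outcomes could lead patients and physicians to abandon the intervention. It does not ask for an interval. My inference is that a non-significant result cannot speak to that worry without one.

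**Working it through.** **Inputs.** From section 5.1 (Sample Size): 66 analysed per group, 85 enrolled per group, 80% followed up at 6 months (85 × 0.8 = 68). From section 5.6: level 0.05, identity link, compound symmetry. Assumed, because the documents give nothing for these outcomes: SD 1; baseline to 6-month correlation r = 0.3 / 0.5 / 0.7; where an effect is needed, d = 0.35 SD, borrowed from the primary outcomes; two-sided tests. Triplets below follow the order of r.

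**The plan's own figure.** The plan has no sample size for the secondary outcomes. The 66 is for the primary outcomes. A single two-sided t-test at 0.35 needs 130 per group; multiplying by a two-measurement factor (1 + 0.008)/2 gives 65.5, rounded up to 66. That route is inferred, not stated, and nothing below depends on it beyond using 66 as n.

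**1. What the group term targets after the drop.** Let D0 and D6 be the between-group differences at baseline and 6 months. Randomisation gives E(D0) = 0; E(D6) = d.
- Complete pairs: the group term is (D0 + D6)/2, with expectation d/2. For d = 0.35 this is 0.175. The ratio 0.50 needs no assumption about d or r.
- 85 per arm at baseline and 68 at 6 months, no imputation: generalised least squares gives baseline more weight, and the weight on D6 is 0.43 / 0.42 / 0.41.
- With multiple imputation, which the plan allows ("a multiple imputation method will be used to impute the missing values if necessary"), simulation gives 0.50 / 0.51 / 0.49.

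**2. Precision of the difference in change (reading b).**
- 66 pairs per arm: SE = √(2(1−r) × 2/66) = 0.206 / 0.174 / 0.135. Multiplied by t(130), this gives a 95% half-width of 0.41 / 0.34 / 0.27 SD.
- 85 and 68 per arm: variance = 2[(1−r²)/68 + (1−r)²/85], half-width 0.38 / 0.33 / 0.26 SD.

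An estimate of exactly zero would therefore leave a worsening of up to that size within the interval.

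**3. How often the term is dropped.** This is one minus the power of the change-score test (noncentral t, 66 pairs per arm):

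| True d (SD) | r = 0.3 | r = 0.5 | r = 0.7 |
|---|---|---|---|
| 0.20 | 84% | 79% | 69% |
| 0.35 | 61% | 49% | 27% |
| 0.50 | 33% | 19% | 4% |

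With 85 and 68 per arm, the row for d = 0.35 becomes 57 / 45 / 24%.

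**4. Consequences under reading (a) only.**
- The group term has SE √((1+r)/66) = 0.140 / 0.151 / 0.160 around 0.175. With equal variances it is independent of the change. Its 95% CI contains the true 0.35 in 76 / 79 / 81% of dropped trials.
- If either term may be claimed as a success, the false-positive rate is 1 − 0.95² = 9.75%.
- The plan also says "Baseline variables that are strongly associated with the outcomes will also be included in the corresponding outcome models". If that brings in the baseline score as a covariate as well as a response, coverage among dropped trials falls to 23 / 7 / 0.1% and the two-step error is 7.7 / 7.2 / 6.7%. The text permits this model but does not specify it.

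**5. The primary models.** Baseline is not a time level, so this dilution does not arise. The same rule would still replace the 6-month contrast with a 6- and 12-month average, although section 5.5 places the primary outcomes at 6 months and makes 12-month use secondary. Illustration with assumed cessation of 10% in controls at both visits and 25% with the intervention at 6 months: the 6-month OR is (0.25/0.75)/(0.10/0.90) = 3.00. After a drop, the model targets 3.0 if the intervention rate at 12 months stays at 25%, about 2.6 at 20%, 2.3 to 2.4 at 15%, and 2.0 to 2.2 at 10%.

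Non-identity links for the secondary outcomes were not computed.

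**The case against.** The strongest reply is that section 5.6 promises no estimate or interval for any outcome, so the silence is general. Checking the interaction means fitting it, so its estimate will exist and a competent analyst would report it. This stands in part: the plan does not say the interval will be withheld, only that nothing commits to reporting it. But the drop rule is a stated instruction about which model is final, and it removes the one term that carries the hypothesis.

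Second, no passage says the remaining group term will be read as the effect. The halving, the coverage figures and the inflated error all need reading (a), and the error figure also needs success to be claimed on either term. That is correct, and those numbers are conditional.

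Third, the half-widths in step 2 describe the trial's precision, which the fix changes little: a baseline-adjusted comparison with 66 per arm has SE 0.166 / 0.151 / 0.124, so a half-width of about 0.33 / 0.30 / 0.25 SD. Also correct. The gain is that the estimate and interval are always part of the planned result.

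Fourth, the t-test or Wilcoxon line might supply an unadjusted 6-month comparison. Both model descriptions take their covariates from the bivariate analysis, so covariate screening is the likelier reading. On either reading, that line promises no 6-month estimate or interval.

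**Conclusion.** The concern holds. For the three secondary outcomes, the written rule removes the term that is the hypothesis whenever it is non-significant, and no other text secures a 6-month between-group difference. This follows from the model and needs no assumed effect size.

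The size depends on the reading. Under (a), with an identity link, the reported term targets half of the effect with complete or imputed data. Under (b), the estimate is unbiased but not committed to. At an assumed 0.35 SD, one of these situations would arise in roughly a quarter to three-fifths of trials for correlations of 0.7 down to 0.3.

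The primary conclusion is not affected by this point. The averaging over 6 and 12 months in the primary models is a lesser, related matter, and it causes no distortion if the effect persists unchanged. The change should be made before analysis.

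**What to change.** In section 5.6, delete the drop rule for the secondary outcomes. Name the 6-month between-group difference as the treatment effect for each, and state that it is always reported with its 95% CI, whatever the interaction p-value. Estimate it from the 6-month score adjusted for the baseline score (ANCOVA), or from a constrained longitudinal model with a common baseline mean. Always keeping and reporting the interaction is acceptable but less efficient. Add one sentence that the 6-month contrast is always reported for the primary outcomes.

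The cost is a few lines, since the baseline scores are already collected. ANCOVA uses only participants with a 6-month score unless the multiple imputation already allowed is applied; the constrained model uses everyone with a baseline score. The fix does not guarantee significance: at an assumed 0.35 SD and 66 per arm, ANCOVA has power of about 55 / 63 / 80% for r = 0.3 / 0.5 / 0.7.

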5.7 Withdrawal of Subjects

We do not anticipate withdrawing participants without their consent for this aim. However, should a participant voluntarily withdraw from the study, we will seek their permission to use their data in the analysis. Should they not agree, we will remove their data from the analysis and store their data with study records. We do not plan to follow-up with participants who are withdrawn by study staff or voluntarily withdraw from the study. Per VA, participation in research is voluntary and study participants will not lose any benefits to which they are entitled and will continue to receive care. Should a Veteran be withdrawn from the study, we will be clear in communicating with the Veteran that they are still eligible for VA care.

6.0 Reporting

Should an adverse event occur, study staff will complete a study form that will include the participant's study number and all relevant information about the adverse event. All staff will be required to immediately notify [name] about the occurrence of a serious or significant adverse event. Upon notification of the adverse event, [name] will take the appropriate action. A study nurse will be available to assess and take appropriate action. For example, if the adverse event is a medical issue (e.g., participant concern about symptoms of medication withdrawal), [name] or the study nurse will immediately notify the staff physician, [name] about the concern. [name] will contact the participant to address any concern and provide medical advice and recommendations, if needed. Following this contact, [name], a study nurse or [name] will follow-up with the participant within 24 hours of the initial contact. This protocol will apply for both CAVHS and Minneapolis VAMC sites.

[name] will also be responsible for reporting any protocol deviations to IRB within 24 hours of their occurrence Case Report forms will be completed immediately by the study personnel responding to the event and submitted to the IRB within 24 hours of the occurrence.

An annual report will be submitted to the local Institutional Review Board and project officer summarizing all adverse events. These procedures for reporting adverse events will apply to adverse events occurring during the baseline, follow-up phases of the clinical trial and during the conduct of the process evaluation.

7.0 Privacy and Confidentiality

This study will access PHI for recruitment under a waiver of HIPAA authorization. This study will collect PHI from study participants with their authorization. PHI will include names and social security numbers. All PHI collected will be stored in locked cabinets under triple lock (cabinet, office, front door). Study staff collecting and storing PHI will be trained in steps to maintain participants' data security (e.g., using secure methods for storage such data). Any electronic PHI (e.g., birthdates) will be stored on an encrypted, password protected server behind the VA firewall. PHI will be coded and maintained in data crosswalk that will also be stored on an encrypted, password protected server. Research Investigator files will be destroyed six years after the end of the fiscal year when the research project has been completed per Records Schedule DAA-0015-2015-004. The ISSO/PO and ACOS/RD will be notified immediately if there is inadvertent loss or disclosure of research data.

8.0 Communication Plan

This protocol and all related documents shall be approved by the IRB and R&D Committee prior to enrollment of any subjects. The informed consent process shall be conducted only by appropriately qualified study personnel. The privacy and confidentiality of subjects shall be respected by all study personnel. The research team will regularly meet to discuss the study's progress and address any adverse events or unanticipated issues. The study coordinators will ensure all applicable IRB and RDC approvals are in place and will be in continuous communication with the principal investigators, Drs. [name] and [name].

